# 5.2 Sample Size Estimation/Accrual Rate

It is anticipated to accrue 1-2 patients per month.

Sample size = 53 evaluable patients, 58 maximum patients (estimating 5 inevaluable patients)

### **5.3** Randomization and Stratification Factors

None.

## **5.4** Evaluation of Efficacy

Patients will be re-staged every 2 cycles of therapy. 1 cycle = 21 days or 3 weeks. Imaging studies will consist of *any* of the following studies: PET-CT scans, chest CT scans, abdominal-pelvic CT scans. Modified RECIST (preferred) or RECIST (if modified RECIST cannot be used) measurements will be performed after every 2 cycles of therapy. The radiologist or the PI will review and determine response based on the RECIST and the data will be documented in the Case Report Form (CRF). Examples of these measurements are described in Tsao et al.[1]

The primary objective of this study is to assess the efficacy of alisertib in pretreated patients with unresectable malignant mesothelioma (pleural or peritoneal). The primary endpoint is the disease control rate at 4 months in patients with unresectable malignant pleural mesothelioma (MPM) treated with alisertib. The trial will be conducted by the Simon's minimax two-stage design and the disease control rate at 4 months will be estimated accordingly (Simon, 1989).

Standard RECIST measurement definitions will be used.

Complete Response (CR): Complete disappearance of all measurable and non-measurable disease. No new lesions.

Partial Response (PR): Greater than or equal to 30% decrease under baseline of the sum of longest diameters of all target measurable lesions. No unequivocal progression or non-measurable disease. No new lesions.

Stable disease (SD): Does not qualify for CR or PR or Progression.

Progression (PD): One or more of the following must occur: 20% increase in the sum of longest diameters of target measurable lesions over smallest sum observed (over baseline if no decrease during therapy). Unequivocal progression of non-measurable disease in the opinion of the treating physician (an explanation must be provided). Appearance of any new lesion/site. Death due to disease without prior documentation of progression and without symptomatic deterioration.

## 5.5 Evaluation of Safety

Patients will be evaluated with a history and physical exam during each clinic visit. Baseline laboratory values will be obtained during each clinic visit. All toxicities reported will be recorded by the research RN and graded using the National Cancer Institute Common Terminology Criteria for Adverse Events (NCI CTCAE), Version 4.03, effective 14 June 2010 (16). These criteria are provided in the Study Manual and are available online at http://ctep.cancer.gov/protocolDevelopment/electronic applications/ctc.htm.

#### **5.6** Correlative Studies

Blood Specimens will be collected at baseline (pretreatment), cycle 3 – day 1 and at progression and banked at MD Anderson Cancer for subsequent analysis. At each time

point, blood will be collected into three (3) x 8 mL EDTA Vaccutainer top tubes separated; plasma and buffy coat will be collected and stored at -70 until analysis.

Pleural Effusion Fluid: in cases when pleural effusion fluid is available, a 10 mL aliquot of the pleural effusion fluid will be collected in a sterile container, aliquoted and stored at -70C until analysis.

Patients must have either archived baseline tumor specimens available and adequate for biomarker analysis or must undergo a tumor tissue biopsy. Tumor specimens will be batched until the end of the clinical trial and subsequently evaluated for aurora kinase pathway molecules by immunohistochemistry, fluorescent in situ hybridization (FISH) for c-myc gene amplification, and next-generation sequencing. Correlation of biomarkers to patient demographics and clinical outcome will be analyzed by the below statistical analysis.

Descriptive statistics including mean, standard deviation, median, and range will be provided for continuous variables such as age. Frequency tables will be used to summarize categorical variables such as gender, and response. The standard error and confidence interval on estimating the disease control rate will be provided. The distribution of time-to-event endpoints, such as time to progression and overall survival, will be estimated using the method of Kaplan and Meier. Comparison of time-to-event endpoints by important patient characteristics will be made using the log-rank test. Cox proportional hazard regression will be employed for multi-covariate analysis on time-to-event outcomes when appropriate.

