### 5. STATISTICAL PROCEDURES

## 5.1 Study Design and Overview of Primary and Secondary Endpoints

The primary objective of this study is to:

• Assess 4-month disease control rate (DCR) in pre-treated patients with unresectable MPM treated with alisertib

The secondary objectives of this study are to:

- To assess the response rate (confirmed and unconfirmed complete + partial responses)
- To assess the progression-free survival.
- To assess overall survival.
- To evaluate the side effects and toxicities associated with this treatment regimen.
- To collect archival tissue, blood, pleural effusion and plasma for correlative studies.

The primary endpoint is the disease control rate at 4 months in patients with unresectable malignant pleural mesothelioma (MPM) treated with alisertib. The trial will be conducted by the Simon's minimax two-stage design and the disease control rate at 4 months will be estimated accordingly (Simon, 1989)

It is assumed that the new regimen will have a target disease control rate of 50% at 4 months. A disease control rate of 30% or lower is considered a failure and the new regimen will be rejected under this circumstance. When the probability of accepting a "bad" regimen (i.e. disease control rate<=30%) is 0.05 and the probability of rejecting a "good" regimen (i.e. disease control rate >=50%) is 0.10, Simon's minimax design requires to enter 24 patients in the first stage. If 7 or less patients are free of disease progression to the treatment at 4 months, the trial will be stopped and the regimen will be declared as ineffective. If there are 8 or more patients are alive and progression-free at 4 months, 29 more patients will be entered in the study to reach a total of 53 patients. By the end of the study, the new regimen will be rejected if disease control rate is less than or equal to 21/53 and will be accepted otherwise. The operating characteristics of the trial are given as follows. When the true disease control rate is 0.30 the probability of stopping the trial early is 57%. On the other

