## 5.6.1.1. Immunohistochemistry

Standard immunohistochemistry (IHC) will be conducted on tumor tissue slides for aurora kinase pathway biomarkers. The precise antibodies are to be determined. A general methodology for standard IHC is described below.

We will perform standard IHC studies of aurora kinase pathway biomarkers and evaluate them in subcellular locations (cytoplasmic, stromal, membrane, and nuclear. The histology sections will be incubated with primary antibodies TBD for a predescribed amount of time at room temperature. Tissue sections will then be incubated with the secondary antibody (TBD) for 30 min, after which diaminobenzidine chromogen was applied for 5 min. Tumor malignant cells and stroma will be evaluated using the same methodology for protein expressions. Briefly, for each marker, two experienced thoracic pathologists ([name] and [name]) will examine both the intensity and extent of immunostaining by light microscopy using a ×20 magnification objective. Immunoreactivity of all antibodies will be detected in the cytoplasm of malignant cell and stroma fibroblast, and in the cytoplasm and nucleus. Cytoplasmic or nuclear expressions will be quantified using a four-value intensity score (0, none; 1+, weak; 2+, moderate; and 3+, strong) and the percentage (0-100%) of the extent of reactivity. A final expression score was obtained by multiplying the intensity and reactivity extension values (range, 0-300).

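### Section 5.6 sends a 0-300 IHC score to a log-rank test with no cut-point; a continuous analysis would keep about 20 points of power and remove the option of a data-chosen cut

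*Combined protocol and SAP*

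**What the plan says.** Section 2.3 lists aurora-pathway tissue biomarkers as an exploratory objective. Section 5.6 sets the timing: "Tumor specimens will be batched until the end of the clinical trial and subsequently evaluated for aurora kinase pathway molecules by immunohistochemistry". Section 5.6.1.1 describes the reading. Two thoracic pathologists "will examine both the intensity and extent of immunostaining by light microscopy", grading intensity from 0 to 3+ and extent from 0 to 100%. Then: "A final expression score was obtained by multiplying the intensity and reactivity extension values (range, 0-300". The antibodies are still to be chosen, and four tissue or subcellular locations are named.

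For the analysis, Section 5.6 refers the correlation of biomarkers with clinical outcome to the paragraph that follows it. That paragraph repeats the general efficacy text of Section 5.1: descriptive summaries, frequency tables, an interval for the disease control rate, Kaplan-Meier curves, and "Comparison of time-to-event endpoints by important patient characteristics will be made using the log-rank test". Its last sentence allows Cox regression for analyses with several covariates where this is judged appropriate.

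The documents give no IHC cut-point, no rule for choosing one, no significance level for the biomarker tests and no statement on whether the pathologists see outcome data. For c-myc the plan does fix a threshold: the Copy Number Analysis text under Section 5.6.1.2.1 defines copy-number gain as at least four copies.

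**The concern.** The listed methods do not fit the measurement. A log-rank test compares groups, and the IHC result is an ordered score with many possible values. To use the named test, someone has to split the score, and by then the outcomes will be known. There are two ways to do that. A split at the median, fixed beforehand, keeps the error rate but discards information in a sample of at most 53 evaluable patients. A split chosen because it separates the curves best inflates the error rate. The plan does not say which route applies.

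There is also a gap at the endpoint that matters most here. Four-month disease control is binary, and nothing in the paragraph relates a score to it.

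Aurora-kinase expression is part of the biological rationale in Section 1.6, and Section 5.6 calls for a biopsy from patients without adequate archived tissue. The analysis of that tissue should therefore be as informative as the sample allows.

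**Working it through.** **The plan's own figure.** N = 53 comes from the Simon minimax design in Section 5.1 (stop at 7 or fewer of 24; reject at 21 or fewer of 53). The exact binomial calculation gives early-stop probabilities of 0.565 at a rate of 0.30 and 0.032 at 0.50. Expected sizes are 24 + 29 × (1 − 0.565) = 36.6 and 24 + 29 × (1 − 0.032) = 52.1. Attained alpha is 0.047 and power 0.902. All agree with the plan. The design sizes the disease-control decision only; it sets no power or alpha for biomarkers.

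**Inputs for the biomarker check.** From the documents: N = 53 (Section 5.2), or 24 if the trial stops at stage 1. Both are upper bounds, since they suppose usable tissue from every patient. Assumed: two-sided 5% per marker, about 14-15% censoring, exponential event times, and for power a hazard ratio of 1.5 per SD of score.

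**Power, by hand.** With about 86% events, D = 53 × 0.86 = 45.6. For a continuous, roughly normal score in a Cox model, z = ln(1.5) × √D = 0.405 × 6.75 = 2.74, so power ≈ Φ(2.74 − 1.96) = Φ(0.78) = 78%. A median split keeps a fraction 2/π of the information, so z = 2.74 × √0.637 = 2.18 and power ≈ Φ(0.22) = 59%.

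Simulation comes out slightly lower, as expected in a small sample:

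| N | Continuous score, Cox | Median split, log-rank |
|---|---|---|
| 53 | 70-76% | 51-56% |
| 24 | 39-44% | 26-29% |

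The ranges span several runs; those at N = 53 include both untied and tied scores. Part of the spread is Monte Carlo error: a run of 500 replicates has a standard error of √(0.73 × 0.27/500) = 2.0 points.

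**False positives if the cut is chosen on the data.** The Miller-Siegmund approximation for a cut searched between quantiles e and 1 − e is 4φ(z)/z + φ(z)(z − 1/z) ln[(1 − e)²/e²]. With z = 1.96 and φ(z) = 0.0585, the first term is 0.119 and the multiplier of the logarithm is 0.0847:
- e = 0.10: 0.119 + 0.0847 × 4.39 = 49%
- e = 0.20: 0.119 + 0.0847 × 2.77 = 35%
- e = 0.25: 0.119 + 0.0847 × 2.20 = 31%

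Simulation of the log-rank test itself, N = 53, 15% censoring, 20,000 replicates per cell:

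| Score | e = 0.10 | 0.15 | 0.20 | 0.25 |
|---|---|---|---|---|
| Untied | 42% | 37% | 31% | 26% |
| 5% steps, 10% zeros | 35% | 32% | 27% | 22% |
| 10% steps, 30% zeros | 27% | 24% | 22% | 19% |
| Cut nearest the median, fixed | 5.4-5.8% in all runs | | | |

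Ties matter because intensity times percent takes repeated values, including zeros. The range is therefore about 19-42% per marker, against about 5.5% for a cut fixed in advance. At N = 24 the same settings give 20-41%.

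**The case against.** The strongest reply is that this is an exploratory analysis with antibodies still to be chosen, so fixing an IHC threshold now would be premature. No patient selection, stopping rule or efficacy claim depends on it. Cox regression is already listed and can take a continuous score, so a split is not unavoidable. The trial was not sized for biomarkers, and with 24 patients either analysis has low power. All of this stands. It limits the weight of the point, but it does not tell the analyst what to do with the score: the Cox route is discretionary and described for multi-covariate work, while the only stated comparison needs groups. A continuous primary analysis needs no threshold, so the undecided antibodies are no obstacle to it.

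Three stronger readings are tempting, and the documents do not support them. A reader might infer that the slides will be scored unblinded; Sections 5.6 and 5.6.1.1 are silent on this, and Section 5.4 gives response assessment to the radiologist or the principal investigator, not to the pathologists. A reader might infer that the biomarker tests carry a false-positive rate near 36%; that is one point in a range, close to the result for an untied score and a particular search, and it applies only if the cut is chosen on the data, which the plan nowhere says. A reader might also infer that a spurious predictive marker would result; a single-arm trial cannot separate predictive from prognostic markers, whatever the cut.

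The per-SD Cox model has its own cost: it assumes a log-linear effect, which may fit poorly with many zero scores. A cut fixed in advance, or a p-value corrected for maximal selection, would also control the error rate.

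**Conclusion.** The point holds as a cheap improvement to an exploratory analysis. The plan pairs a 0-300 score with a test that needs groups, gives no cut-point, does not state reader blinding, and names no method for 4-month disease control. An honest median split costs about 20 points of power at N = 53 (roughly 51-56% against 70-76%) and about 13-15 at N = 24. These figures rest on the assumed hazard ratio of 1.5 per SD, the assumed censoring and tissue from every patient. The error inflation to roughly 20-40% per marker is conditional on a data-chosen cut and on an assumed two-sided 5% level. It does not count the undecided number of antibodies, the four locations or the several endpoints. The Simon decision on disease control is not affected.

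**What to change.** In Section 5.6, replace the log-rank step for IHC with a stated primary biomarker analysis:
- Enter each IHC score as a continuous covariate, per SD, in a Cox model for PFS and in one for OS.
- Enter the same score in a logistic model for 4-month disease control.
- Use a median split only to display Kaplan-Meier curves.

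In Section 5.6.1.1, state that the two pathologists receive coded slides without outcome data. The same edit could say how their two readings become one score and that the antibodies are listed before staining begins.

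The cost is a few sentences and slide labels; no new visit, sample or procedure is needed. The downside is that results are reported per SD rather than as high versus low, and that the model assumes a log-linear effect.

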### 5.6.1. Tissue Biomarker Analysis

A total of 10 unstained slides or a tumor block will be requested from each patient. Archived baseline tissue blocks or unstained slides will be accepted. If no baseline tissue is available, then patients will be asked to undergo a tumor tissue biopsy. The tumor tissue will be subjected to immunohistochemistry analysis of aurora kinase pathway biomarkers and fluorescent in situ hybridization analysis of the copy numbers of the c-myc gene.

## 5.6.1.1. Immunohistochemistry

Standard immunohistochemistry (IHC) will be conducted on tumor tissue slides for aurora kinase pathway biomarkers. The precise antibodies are to be determined. A general methodology for standard IHC is described below.

We will perform standard IHC studies of aurora kinase pathway biomarkers and evaluate them in subcellular locations (cytoplasmic, stromal, membrane, and nuclear. The histology sections will be incubated with primary antibodies TBD for a predescribed amount of time at room temperature. Tissue sections will then be incubated with the secondary antibody (TBD) for 30 min, after which diaminobenzidine chromogen was applied for 5 min. Tumor malignant cells and stroma will be evaluated using the same methodology for protein expressions. Briefly, for each marker, two experienced thoracic pathologists ([name] and [name]) will examine both the intensity and extent of immunostaining by light microscopy using a ×20 magnification objective. Immunoreactivity of all antibodies will be detected in the cytoplasm of malignant cell and stroma fibroblast, and in the cytoplasm and nucleus. Cytoplasmic or nuclear expressions will be quantified using a four-value intensity score (0, none; 1+, weak; 2+, moderate; and 3+, strong) and the percentage (0-100%) of the extent of reactivity. A final expression score was obtained by multiplying the intensity and reactivity extension values (range, 0-300).

## 5.6.1.2. c-myc copy number analysis rationale for study

We[18] have previously evaluated potential therapeutic targets for malignant pleural mesothelioma (MPM) and one of the most common chromosomal amplification sites in cancer tissues is the 8q24 region which contains the genes C-MYC and PVT1 [19-21]. C-MYC encodes a transcription factor that regulates the expression of multiple genes involved in cellular responses such as growth, proliferation, apoptosis, and differentiation [22, 23]. Deregulated amplification and expression of the MYC locus occurs in ~30% of human cancers, including colon, prostate and breast carcinomas, and has been associated with poor prognosis [19, 24, 25]. PVT1 is a candidate oncogene located adjacent to the MYC locus on chromosomal region 8g24 [25-27]. PVTI has been shown to act as a non-coding RNA with many alternatively spliced isoforms [20]. The PVT1 locus has recently been found to contain a cluster of at least six microRNAs (miRNAs) (miR-1204, -1205, -1206, -1207-3p, -1207-5p, and -1208) that span the PVT1 region, adding further complexity to the locus [20]. PVT1 copy number gains (CNGs) and PVT1 overexpression both have been implicated in the pathophysiology of many tumors, including breast and ovarian cancers and acute myeloid leukemia [26, 28]. Additionally, PVT1 alteration has been shown to contribute to tumor survival and chemoresistance [28, 29].

We sought to elucidate these roles and the specific mechanisms of action of *C-MYC* and *PVT1* involved in the pathogenesis of malignant pleural mesothelioma (MPM) by characterizing the molecular abnormalities found in the 8q24 locus in malignant pleural mesothelioma (MPM) cell lines and in specimens from surgically resected malignant pleural mesotheliomas. The *miRNA* (*miR-1204*, -1205, 1206, -1207 3p, 1207-5p, and -1208) expression in malignant pleural mesothelioma (MPM) cell lines was evaluated. We also determined the biological impact of siRNA-mediated *C-MYC* and *PVT1* abrogation on malignant pleural mesothelioma (MPM) cellular processes such as apoptosis, cell proliferation, and response to cisplatin and then determined the effect of *C-MYC*, *PVT1*, and *miR-1204 knockdown* on the expression levels of apoptosis related genes. Finally, we studied *C-MYC* and *PVT1* copy number and gene expression in malignant pleural mesothelioma (MPM) tumor specimens.[18]

Our copy number analysis revealed copy number gains (CNGs) in chromosomal region 8q24 in three of five malignant pleural mesothelioma (MPM) cell lines. MicroRNA analysis showed high *miR-1204* expression in MSTO-211H cell lines with ≥4 copies of *PVT1*. Knockdown by siRNA showed increased PARP-C levels in MSTO-211H transfected with *siPVT1* but not in cells transfected with si*C-MYC*. *C-MYC* and *PVT1* knockdown reduced cell proliferation and increased sensitivity to cisplatin. Analysis of the expression of apoptosis-related genes in the MSTO-211H cell line suggested that *C-MYC* maintains a balance between pro-apoptotic and anti-apoptotic gene expression, whereas *PVT1* and to a lesser extent *miR-1204*, upregulate pro-apoptotic genes and downregulate anti-apoptotic genes. FISH analysis of malignant pleural mesothelioma (MPM) tumor specimens showed a high frequency of both CNGs (11/75) and trisomy (three copies; 11/75) for the *C-MYC* locus.[18]

We additionally determined C-MYC and PVT1 mRNA expression levels in a subset of 55 malignant pleural mesothelioma (MPM) tumor specimens paired with 41 normal tissues from our database using Affymetrix U133 plus 2.0 chips. We found significant differences in C-MYC and PVT1 gene expression between the normal tissues and the tumor samples (Fig. 3F and 3G; p < 0.05).

Our preclinical results suggest that *C-MYC and PVT1* amplification promotes a malignant phenotype of malignant pleural mesothelioma (MPM), with *C-MYC* amplification stimulating cell proliferation and *PVT1* both stimulating proliferation and inhibiting apoptosis.

This is significantly relevant to this protocol as c-myc expression and pathway upregulation has been identified as a potential biomarker in aurora kinase inhibition in other tumor types (personal communication Millennium).

5.6.1.2.1. Methodology c-myc copy number analysis measured by quatitative PCR and fluorescence in situ hybridization (FISH)

## **Isolation of DNA and Copy Number Profiling**

DNA was extracted from cell lines using DNAzol Reagent (Life Technologies, Grand Island, NY) and whole-genome single nucleotide polymorphism (SNP) array profiling can be performed using Affymetrix SNP 6.0 chips (Agilent Technologies, Santa Clara, CA). Copy number gains (CNGs) were identified using the SNP-Fast Adaptive States Segmentation Technique 2 algorithm in Nexus 5.1 software (BioDiscovery, Hawthorne, CA) with the significance threshold for segmentation setting at  $p < 5 \times 10^{-7}$ . CNGs were defined with log2 ratio values of 0.2, and two or more than two CNGs were defined by log2 ratio values of 0.7.

# **Copy Number Analysis**

We used fluorescence in situ hybridization (FISH) and real-time quantitative PCR (q-PCR) to quantify 8q24 CNGs in malignant pleural mesothelioma (MPM) tumor specimens. We used directly labeled fluorescent chromosomal centromeric probes (CEP 8, SpectrumGreen) for chromosome 8 and locus-specific probes (LSI) for regions 8q24.12-q13 (*C-MYC* Spectrum Orange) (Vysis, Abbott Laboratories, Chicago, IL). Fluorescence in situ

hybridization (FISH) was performed according to the manufacturer's instructions. Copy number analysis was performed in 50 nuclei per tumor in at least four areas. Copy number alteration was defined as the presence of more than two gene copies per cell on average of the 50 cells. Trisomy was defined as the presence of three copy number alterations and CNG was defined the presence of at least four copies. To enrich for malignant cell content for q-PCR analysis, tumor tissues were manually microdissected for subsequent DNA extraction from FFPE tissue sections. Tumor DNA was extracted using the Pico Pure DNA Extraction Kit (Arcturus, Life Technologies, Grand Island, NY) according to the manufacturer's instructions. DNA samples with proportions of microdissected tumor cell greater than 70% were qualified for qPCR analysis. *MYC* and *PVT1* gene copy numbers were examined by q-PCR using the ABI 7300 real time PCR system (Applied Biosystems, Grand Island, NY). A gene copy number ≥4 was considered as CNG [30].

